### 3.2.2. Secondary endpoint(s)

#### Key secondary endpoints:

- Castration-resistant prostate cancer (CRPC)-free survival, defined as the time from randomisation to onset of CRPC according to PCWG3 criteria, or death, whichever occurs first.
- Clinical progression-free survival, defined as time from randomisation to first occurrence of any one of the following:
  - Cancer pain deterioration (2-point deterioration from baseline according to the Brief Pain Inventory - Short Form [BPI-SF] questionnaire, or initiation of opioid therapy, or a  $\geq 30\%$  increase in opiate use),
  - Any deterioration of physical function measured using the 4-IADL assessment tool,
  - A deterioration in ECOG performance status of at least 2 points from baseline,
  - Death from any cause.
- Overall survival, defined as the time from randomisation to the time of death from any cause. For subjects alive at the time of analysis, data will be censored on the last date the subject was known to be alive or lost to follow-up or withdraw consent.
- Toxicity will be evaluated according to version 5 of the National Cancer Institut - Common Terminology Criteria for Adverse Events (NCI-CTCAE v5.0).

#### Other secondary endpoints

- Time to worsening in prostate cancer-related urinary symptoms, defined as an increase from baseline of greater or equal to 8 points in the urinary symptom scale/score (PRURI) measured using the prostate cancer module of the European organisation for research and treatment of cancer (EORTC) quality of life questionnaire (QLQ) (EORTC-QLQ-PR25).
- Time to next symptomatic skeletal event, defined as the time from randomisation until first occurrence of one of the following: a symptomatic fracture, radiation or surgery to bone or a spinal cord compression (PCWG3 criteria).

**Note:** *The occurrence of these events will be determined by investigator evaluation. No systematic X-Ray will be performed.*

- Complete PSA response (defined as PSA  $\leq$  0.2 ng/ml) at 6 months.
- Prostate cancer-specific survival, defined as the time from randomisation to the date of death due to prostate cancer (deaths due to other causes will be censored).
- Time to deterioration for EORTC QLQ-PR25 symptom subscales, defined as the first decline in the HRQoL score from baseline equal to or greater than the minimally important difference (MID; a measure of clinical significance) defined as half the standard deviation of the baseline value for each subscale.
- Time to first subsequent systemic anti-cancer therapy (SACT) defined as the time from randomisation to the date of initiation of any SACT for CRPC, following initiation of the study treatment.
- Efficacy of subsequent SACT will be assessed according to rPFS, OS, and PFS after next line of treatment (PFS2); defined as the time from randomisation to second objective disease progression, or death from any cause, whichever first.
- Health related quality of life will be evaluated using the EORTC-QLQ-C30, EORTC-QLQ-PR25 and BPI-SF questionnaires.
- Geriatric status will be evaluated using the Geriatric Core Dataset (G-Code) assessment.
- Impact of sarcopenia on overall survival will be evaluated by comparing the distribution of overall survival between sarcopenic and non-sarcopenic patients.
- Impact of sarcopenia on treatment response will be evaluated by comparing rate of response in sarcopenic and non-sarcopenic patients.

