#### STATISTICAL ANALYSIS:

For primary and secondary efficacy endpoints, the analysis will be performed on the ITT population, i.e. all randomised patients will be included, whether eligible or not, compliant or not. Patients will be analysed according to their randomisation arm, regardless of the actual treatment received.

Analysis of the primary endpoint will be event-driven. Time to event endpoints will be reported using the Kaplan-Meier method with Rothman's 95% confidence intervals. A log-rank test will provide the statistical significance of the randomised treatment effect. Additionally a Cox model will provide an estimate of the randomised treatment effect (hazard ratio).

Stratification factors will include: LATITUDE risk criteria (high risk versus low risk, [Fizazi, 2017](#)) and ECOG performance status score (0 or 1 vs. 2).

Qualitative data will be expressed as percentages and compared between the treatment groups using the chi-square test (or the Fisher exact test). Quantitative data will be expressed as means and standard deviation (or medians and range) and compared between the treatment groups using the Student t-test (or the Wilcoxon test).

The analysis of the secondary endpoints will be performed using a formal adjustment for multiple testing.

One interim analysis will be performed after observing at least 70% of the number of expected events (i.e. at least 138 events). Stopping rules using the spending function approach of Lan and DeMets with O'Brien-Fleming type spending function will be followed to conclude at each sequential analysis.

Nominal p values for overall type I error of 0.05 Lan-DeMets boundaries are:

- Efficacy interim analysis (138 events, i.e. 70% expected events): p-value to reject  $H_0 \leq 0.015$  (equivalent to the stopping boundaries Z-Scale:  $\pm 2.437$ )
- Final analysis (197 events, i.e. 100% expected events): p-value to reject  $H_0 \leq 0.045$  (equivalent to the stopping boundaries Z-Scale:  $\pm 2.0$ )

The results of the interim analyses will be given only to the IDMC members.

Safety analysis will be summarized on the Safety Population (i.e. all patients who receive any part of investigational treatment). Incidence of AEs will be summarized by system organ class and preferred term according to MedDRA coding, and will be presented by treatment groups and

overall. AEs will be summarized by grade (NCI CTCAE v5.0), according to the worst grade experienced.

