### 10.1. Statistical hypothesis and sample size determination

The primary evaluation criterion/endpoint for this study is radiographic progression-free survival (Section 3.2.1).

Assuming a median rPFS of 12 months for the control group, a planned sample size of 300 subjects will be required to provide an 85% power to detect at least a HR of 0.65 (median rPFS 12 months in the standard arm versus 18.5 months in the experimental arm) at a 2-tailed significance level of 0.05 and a drop-out hazard rate in both arms of 0.014 (i.e. a maximum 19.3% drop-out rate at the end of study corresponding to non-evaluable or study withdrawal patients).

The number of **randomised patients will be 300 patients** (150 patients per arm). The dropout rate will be monitored during the study and in case of increased drop-out the sample size may be adjusted accordingly.

Based on the randomization rates observed since the inclusion of the first patient and the projected rates according to the opening of investigator sites (see below), patient inclusion-randomisation is expected to be complete in 60 months.

	Number of randomized patients during the period	Cumulative number (cumulative percentage) of randomized patients at the end of the period
March 2022-Feb 2023	18 pts (1.5 pts/months)	18 (6%)
March 2023-Feb 2024	50 pts (4.167 pts/months)	68 (22.67%)
March 2024-Feb 2025	53 pts (4.4 pts/months)	121 (40.33%)
Mars 2025-Feb 2027*	179 pts (7.5 pts per month)*	300 (100%)*

\*Grounded on projections

An additional 15 months following termination of accrual (i.e. a total of 75 months since the randomization of the first patient) is expected to obtain the required 197 events, assuming that events will follow an exponential distribution with a constant hazard rate.

The final analysis is scheduled 10 years after the last patient inclusion-randomisation.

 Based on data from the control arm of the LATITUDE trial (Fizazi, 2017), and taking into account that (i) patients with oligo-metastatic disease (low risk patients) will not be enrolled, and (ii) some patients are expected to die from other causes before they reach a progression endpoint, making the median rPFS probably shorter than that seen in the LATITUDE trial

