The proportional hazard assumption will be assessed graphically by plotting log (-log[estimated survival distribution function]) against log(survival time). The resulting graphs should have approximately parallel lines when the assumption holds. If the proportional hazards assumption is reasonably met, then a stratified Cox proportional hazard model will be used to estimate the treatment effect using Hazards Ratio (HR) and its two-sided 95% confidence interval (95%CI). If the proportional hazards assumption is violated, then the inference remains statistically valid for testing equality in survival distributions. In addition, rPFS will be descriptively summarized using Kaplan-Meier methodology, including medians and two-sided Rothman's 95%CI ([Kaplan, 1958](#); [Rothman, 1978](#)).

Stratification factors will include:

- LATITUDE risk criteria (high risk versus low risk, [Fizazi, 2017](#))
- ECOG performance status score (0 or 1 vs. 2).

If final analysis of the primary endpoint meets the pre-specified hypothesis (see Section 10.1), an additional sensitivity analysis of rPFS will be performed using the results of a centralised disease evaluation by an independent review committee (IRC).

All the other secondary time to event endpoints (namely, CRPC-free survival, clinical progression-free survival, time to worsening in prostate cancer-related urinary symptoms, time to next symptomatic skeletal event, prostate cancer specific survival and overall survival, time to first subsequent SACT and time to second subsequent SACT) will be analysed using the same methods as the primary endpoint (stratified two-sided log-rank test, stratified Cox proportional hazards models). Secondary endpoints will be analysed according to the investigators' assessment of response. Censoring rules for these endpoints will be detailed in the SAP.

The median follow-up will be estimated using the inverse Kaplan-Meier method ([Schemper, 1996](#)).

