#### **10.3.5. Geriatric status**

Patient autonomy will be evaluated using ADL and 4-IADL evaluations. Change over time in ability to perform ADL and IADL will be investigated.

For exploratory purposes, Time to definitive deterioration in ADL will be compared. Time to definitive deterioration of ADL will be defined as the interval between randomisation and the first decline in the ADL score  $\geq 2$  points compared to the ADL at inclusion with no further improvement in score  $\geq 2$  points. Progression or death will be considered as an event.

In a complementary analysis, competing risks approach will be used to decompose Time to definitive deterioration of ADL considering death and progression as a competing event.

Change over time in other geriatric parameters will be investigated.

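### Kaplan-Meier reporting of prostate-cancer-specific survival, with other-cause deaths censored, overstates the probability of dying of prostate cancer

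*Protocol*

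**What the plan says.** Section 3.2.2 and the matching list in the protocol summary define prostate-cancer-specific survival as time from randomisation to prostate-cancer death, with the rule that "deaths due to other causes will be censored". It is one of the other secondary endpoints. Section 10.3.7 treats every endpoint beyond CRPC-free survival, clinical progression-free survival and overall survival as exploratory.

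For reporting, part E of the protocol summary states: "Time to event endpoints will be reported using the Kaplan-Meier method with Rothman's 95% confidence intervals". Section 10.3.2 lists prostate-cancer-specific survival among the secondary endpoints that "will be analysed using the same methods as the primary endpoint (stratified two-sided log-rank test, stratified Cox proportional hazards models"), and then adds: "Censoring rules for these endpoints will be detailed in the SAP".

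Footnote 5 of section 10.1 anticipates competing mortality: "some patients are expected to die from other causes before they reach a progression endpoint". The only competing-risks analysis in the protocol is in section 10.3.5, where a "competing risks approach will be used to decompose Time to definitive deterioration of ADL" as a complement to the main analysis of that endpoint.

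**The concern.** Censoring other-cause deaths is the usual way to set up a cause-specific log-rank test and Cox model. The difficulty lies in the curve and the percentages read from it. A censored patient is treated as someone who could still have the event later, but a man who has died of a stroke cannot later die of prostate cancer. Kaplan-Meier therefore passes his remaining risk to the survivors, and one minus Kaplan-Meier no longer describes the proportion of randomised men who die of their cancer.

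The point carries weight in this trial because eligibility requires a frailty criterion, patients are followed for up to 10 years (section 3.3), and the protocol itself expects non-cancer deaths. In such men, clinicians will read these curves for the absolute risk of dying of the cancer rather than of something else. This is also the one endpoint defined by cause of death.

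**Working it through.** **The plan's own figure.** The protocol gives none for this endpoint: no expected prostate-cancer mortality and no other-cause rate. Its design figures concern rPFS and reproduce. With one look at 138 of 197 events and O'Brien-Fleming-type spending, the boundaries are Z = 2.437 and 2.000, and 197 events give 85.1% power at HR 0.65. They do not depend on this point.

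**Direction of the error.** Write h_pc and h_oc for the cause-specific hazards of prostate-cancer and other-cause death, and H_pc and H_oc for their cumulative hazards.

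- One minus Kaplan-Meier, with other-cause deaths censored, estimates ∫ h_pc(u) exp(−H_pc(u)) du.
- The actual probability (cumulative incidence) is ∫ h_pc(u) exp(−H_pc(u) − H_oc(u)) du.

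The second integrand carries the extra factor exp(−H_oc(u)), which is at most 1. One minus Kaplan-Meier is therefore never below the cumulative incidence, and it exceeds it wherever prostate-cancer deaths follow other-cause deaths.

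**Inputs for the size.**

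- All-cause hazard: the median overall survival of 36.5 months on ADT alone (section 1.2) gives h = ln 2 / 36.5 = 0.01899 per month.
- Share s of deaths from other causes: an assumption, varied from 10% to 50%.
- Constant hazards: an assumption.

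**Formulas.** 1 − KM = 1 − exp(−(1−s)·h·t), and CIF = (1−s)·(1 − exp(−h·t)).

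Example with s = 0.30 and t = 60: (1−s)·h = 0.01329, so 1 − KM = 1 − exp(−0.798) = 55.0%. CIF = 0.70 × (1 − exp(−1.139)) = 47.6%. The gap is 7.4 points.

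| Share s | 3 years: 1−KM / CIF (gap) | 5 years | 10 years |
|---|---|---|---|
| 10% | 46.0 / 44.6 (1.4) | 64.1 / 61.2 (2.9) | 87.1 / 80.8 (6.4) |
| 20% | 42.1 / 39.6 (2.5) | 59.8 / 54.4 (5.4) | 83.8 / 71.8 (12.0) |
| 30% | 38.0 / 34.7 (3.4) | 55.0 / 47.6 (7.4) | 79.7 / 62.8 (16.9) |
| 40% | 33.6 / 29.7 (3.9) | 49.5 / 40.8 (8.7) | 74.5 / 53.9 (20.7) |
| 50% | 29.0 / 24.8 (4.2) | 43.4 / 34.0 (9.4) | 68.0 / 44.9 (23.1) |

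Values are percentages; gaps are percentage points computed before rounding.

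**Second anchor.** Using the 31% 5-year survival in section 1.1.2 instead, the 5-year gap is 3.0 to 9.8 points over the same shares.

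**Effect on the comparison.** A large simulation used s = 30% in the control arm, an assumed cause-specific hazard ratio of 0.70 and administrative censoring. At 5 years the control arm showed 55.0% by one minus Kaplan-Meier and 47.7% by cumulative incidence; the experimental arm showed 42.8% and 36.8%. The absolute difference between arms was 12.2 points by Kaplan-Meier and 10.8 by cumulative incidence. The cause-specific rate ratio came back as 0.699, so the relative comparison was recovered.

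**The case against.** The strongest reply is that little depends on this. The censoring rule is correct for the planned test and hazard ratio. The endpoint is exploratory, and the primary and key secondary efficacy endpoints all count death as an event. All of that stands, and it confines the point to the absolute probabilities of one endpoint.

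The commitment to Kaplan-Meier can also be called thin. Section 10.3.2 spells out the shared methods as the log-rank test and Cox model, and its own Kaplan-Meier sentence names only rPFS. But the general sentence in the summary covers every time-to-event endpoint. Nothing bars a cumulative incidence from being added later, and nothing provides one. The ADL precedent is also limited: death counts as an event in the main ADL analysis, and competing risks enters only as a complement.

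Two stronger readings are tempting, and the protocol does not support them:

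- A reader might infer that symptomatic skeletal events, urinary worsening and time to first subsequent SACT share the fault, since death is not part of their definitions. No section says that death is censored for them, and section 10.3.2 leaves their censoring rules to the SAP, which was not available. No error can be claimed there.
- A reader might infer that a treatment effect on other-cause death would stay hidden. Overall survival is a key secondary endpoint that counts every death, and section 10.3.3 lists deaths. What is missing is only a direct estimate of other-cause death by arm.

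**Conclusion.** The point holds for prostate-cancer-specific survival. The protocol fixes both the censoring and the estimator, and together they overstate the probability of prostate-cancer death whenever other-cause deaths occur. The direction is certain; the size is not, because the protocol gives no other-cause mortality. With median overall survival of 36.5 months, constant hazards and 10% to 50% of deaths from other causes, the overstatement is about 1 to 4 points at 3 years, 3 to 9 at 5 years and 6 to 23 at 10 years. The median comes from a trial population not selected for frailty, so both the all-cause hazard and the share may differ here.

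This is a fault of absolute reporting. The log-rank test and Cox model remain valid for the cause-specific hazard.

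**What to change.** For prostate-cancer-specific survival:

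- Keep the stratified log-rank test and the stratified Cox hazard ratio, labelled as cause-specific.
- Report probabilities and curves by Aalen-Johansen cumulative incidence, with other-cause death as the competing event.
- Show the cumulative incidence of other-cause death by arm beside them.
- Exempt this endpoint from the general Kaplan-Meier sentence in part E of the summary.

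For skeletal events, urinary worsening and time to first SACT, the SAP should state how death is handled. If it censors death, the same estimator should be used.

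The cost is a few lines of wording and standard code. No extra data are needed, since the endpoint already requires cause of death. The reported risks will be lower than Kaplan-Meier would have given.

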#### Other secondary endpoints:

- Time to worsening in prostate cancer-related urinary symptoms, defined as an increase from baseline of greater or equal to 8 points in the urinary symptom scale/score (PRURI), measured using the prostate cancer module of the European organisation for research and treatment of cancer (EORTC) quality of life questionnaire (QLQ) (EORTC-QLQ-PR25).
- Time to next symptomatic skeletal event, defined as the time from randomisation until first occurrence of one of the following: a symptomatic fracture, radiation or surgery to bone or a spinal cord compression (PCWG3 criteria).

**Note:** The occurrence of these events will be determined by investigator evaluation. No systematic X-Ray will be performed.

- Complete PSA response (defined as PSA  $\leq$  0.2 ng/ml) at 6 months.
- Prostate cancer-specific survival, defined as the time from randomisation to the date of death due to prostate cancer (deaths due to other causes will be censored).
- Time to deterioration for EORTC QLQ-PR25 symptom subscales, defined as the first decline in the HRQoL score from baseline equal to or greater than the minimally important difference (MID; a measure of clinical significance) defined as half the standard deviation of the baseline value for each subscale.
- Time to first subsequent systemic anti-cancer therapy (SACT) defined as the time from randomisation to the date of initiation of any SACT for CRPC, following initiation of the study treatment.
- Efficacy of subsequent SACT will be assessed according to rPFS, OS, and PFS after next line of treatment (PFS2); defined as the time from randomisation to second objective disease progression, or death from any cause, whichever first.
- Health related quality of life will be evaluated using the EORTC-QLQ-C30, EORTC-QLQ-PR25 and BPI-SF questionnaires.
- Geriatric status will be evaluated using the Geriatric Core Dataset (G-Code) assessment.
- Impact of sarcopenia on overall survival will be evaluated by comparing the distribution of overall survival between sarcopenic and non-sarcopenic patients.
- Impact of sarcopenia on treatment response will be evaluated by comparing rate of response in sarcopenic and non-sarcopenic patients.

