## Appendix 11. EORTC-QLQ-PR25

### EORTC QLQ - PR25

Patients sometimes report that they have the following symptoms or problems. Please indicate the extent to which you have experienced these symptoms or problems during the past week. Please answer by circling the number that best applies to you.

During the past week:	Not at all	A little	Quite a bit	Very much
31. Have you had to urinate frequently during the day?	1	2	3	4
32. Have you had to urinate frequently at night?	1	2	3	4
33. When you felt the urge to pass urine, did you have to hurry to get to the toilet?	1	2	3	4
34. Was it difficult for you to get enough sleep, because you needed to get up frequently at night to urinate?	1	2	3	4
35. Have you had difficulty going out of the house because you needed to be close to a toilet?	1	2	3	4
36. Have you had any unintentional release (leakage) of urine?	1	2	3	4
37. Did you have pain when you urinated?	1	2	3	4
38. Answer this question only if you wear an incontinence aid: Has wearing an incontinence aid been a problem for you?	1	2	3	4
39. Have your daily activities been limited by your urinary problems?	1	2	3	4
40. Have your daily activities been limited by your bowel problems?	1	2	3	4
41. Have you had any unintentional release (leakage) of stools?	1	2	3	4
42. Have you had blood in your stools?	1	2	3	4
43. Did you have a bloated feeling in your abdomen?	1	2	3	4
44. Did you have hot flushes?	1	2	3	4
45. Have you had sore or enlarged nipples or breasts?	1	2	3	4
46. Have you had swelling in your legs or ankles?	1	2	3	4

Please go to the next page

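### Time to deterioration on the QLQ-PR25 symptom subscales is defined by a fall in score, although a higher score on these scales means more symptoms

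*Protocol*

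**What the plan says.** Section 3.2.2 lists, among the other secondary endpoints, "Time to deterioration for EORTC QLQ-PR25 symptom subscales". The event is "the first decline in the HRQoL score from baseline equal to or greater than the minimally important difference", and that difference is "defined as half the standard deviation of the baseline value for each subscale". The protocol summary repeats the definition with the same direction: "the first decline in the HRQoL score from baseline equal to or greater than the" MID. Only symptom subscales are named; no functioning scale is mentioned.

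The same list has a second endpoint on the same questionnaire, time to worsening of urinary symptoms on the PRURI scale. Its event is an "increase from baseline of greater or equal to 8 points in the urinary symptom scale/score".

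Appendix 11 reproduces the form. Its opening instruction is "Please indicate the extent to which you have experienced these symptoms or problems during the past week", and the answers run from 1 (not at all) through 2 (a little) and 3 (quite a bit) to 4 (very much).

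**The concern.** On a scale where a larger number means more of a symptom, a fall in score is relief. The definition therefore attaches the label deterioration to improvement. It also conflicts with the urinary endpoint a few lines above it, which treats a rise on the same instrument as worsening.

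At stake is the meaning of one patient-reported endpoint. If an analysis program follows the sentence literally, patients who improve enter as events and patients who worsen do not. A difference between arms in symptom relief could then be reported as a difference in deterioration, with the sign wrong. The trial enrols frail men, for whom symptom burden matters to the balance of benefit and harm, so the error would be awkward even in an endpoint of low rank.

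**Working it through.** This is a check of direction. The protocol gives no figure to reproduce for this endpoint, and no sample size, power or alpha calculation depends on it.

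**Step 1: which direction is worse.**

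| Place | What it fixes | Direction of worsening |
|---|---|---|
| Appendix 11, item coding | 1 = not at all, up to 4 = very much | Higher |
| Section 3.2.2 and summary, PRURI endpoint | Rise of at least 8 points | Higher |
| Section 3.2.2 and summary, PR25 symptom subscales | Fall of at least 0.5 baseline SD | Lower |

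The first two agree and the third does not. No section says that symptom scores are reversed before analysis.

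**Step 2: what the literal rule does to a patient.** The protocol gives neither a scoring formula nor a baseline SD, so the example assumes:
- the urinary score is the mean of 8 items, rescaled linearly to 0–100: score = (mean − 1) / 3 × 100;
- the baseline SD is 15, 20 or 25, so the MID of 0.5 × SD is 7.5, 10 or 12.5.

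Both patients start at category 2 on all 8 items: (2 − 1) / 3 × 100 = 33.3.
- Patient A worsens by one category on 4 items: mean 2.5, score 50.0, change +16.7.
- Patient B improves by one category on 4 items: mean 1.5, score 16.7, change −16.7.

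| Rule | A (worse, +16.7) | B (better, −16.7) |
|---|---|---|
| As written: fall ≥ 0.5 SD | No event | Event |
| PRURI endpoint: rise ≥ 8 | Event | No event |
| Corrected: rise ≥ 0.5 SD | Event | No event |

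The result is the same for all three SDs, because 16.7 exceeds 7.5, 10 and 12.5. The assumptions affect only whether a change is large enough to count; the direction depends on neither of them.

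**Step 3: the floor.** A patient who answers not at all to every item of a subscale at baseline has the lowest possible score. Under the literal rule he can never have an event on that subscale, however much he worsens later.

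**The case against.** The intent can be recovered. The endpoint is called time to deterioration, the neighbouring urinary endpoint has the right direction, and a decline in the HRQoL score may be loose wording for worse quality of life. Section 10.3.4 leaves detailed quality-of-life hypotheses to the SAP, which is not at hand, and a sensible programmer might code it correctly. The PRURI endpoint and the planned analyses of change over time would also tend to expose a sign error.

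This stands as a limit on the consequence. It does not rescue the definition. Section 10.3.2 leaves censoring rules to the SAP and Section 10.3.4 leaves hypotheses, but the event itself is fixed in the protocol, and it refers to the score of symptom subscales. An SAP that follows it inherits the error. One that silently reverses it departs from the protocol's stated endpoint.

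The rank of the endpoint also stands as a limit. Section 10.3.7 names three key secondary efficacy endpoints and treats all others as exploratory. The endpoint is also absent from the time-to-event endpoints that Section 10.3.2 assigns to the stratified log-rank test and Cox model, whereas the urinary endpoint is listed there. Section 10.3.7 still provides for each remaining endpoint to be tested at two-sided 0.05, so a nominal comparison remains possible.

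Three stronger readings are tempting, and the documents do not support them:
- **The treatment comparison will be reversed.** That needs literal programming and a real difference in symptom change between arms; Section 10.3.4 expects no significant quality-of-life difference. Nor is time to first decrease an exact mirror image of time to first increase, since one patient can have both.
- **A given share of patients will be misclassified.** The protocol has no baseline SD and no correlation between visits. With no mean change and symmetric changes, the wrong and the right direction would select equal proportions, though different patients.
- **Two cut-offs for urinary symptoms are an error.** Eight points and half an SD coincide only if the baseline SD is 16, but two prespecified thresholds can coexist. Only the opposite directions are a contradiction.

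**Conclusion.** The definition is wrong as written. On the protocol's own item coding, and by its own rule for PRURI, a fall on a symptom subscale is improvement, and both places where the endpoint is defined call it deterioration. Followed literally, the endpoint measures time to symptom relief under the wrong name and contradicts the urinary endpoint in the same list. This conclusion rests on the protocol text alone; the rescaling and SDs in the example are illustrative.

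The effect is confined to one exploratory endpoint tested without multiplicity adjustment. The primary endpoint (rPFS), the sample size, the interim boundaries and the key secondary family are untouched. The harm is conditional on literal programming, and its size cannot be estimated from the protocol. It should be corrected because the sentence cannot be applied as it stands and the correction is simple.

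**What to change.** In the protocol summary and in Section 3.2.2, define the event as the first increase (worsening) in the symptom subscale score from baseline of at least the MID. Keep a decrease as the event only for a functioning scale, if one is added, and name that scale. The SAP and the analysis programs should carry the same direction.

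Whether the urinary subscale stays under both endpoints, and which cut-off applies to it, is for the sponsor to decide and state; the correction does not depend on that choice.

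The cost is a short wording change in two places, made through a protocol amendment, and agreement with the SAP. No new data are needed, because the questionnaire is unchanged. The current amendment reports about 115 of 300 patients enrolled and the trial is double-blind, so the correction can be made before treatment codes are known.
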